8.2.5.3 Injection Site Reactions

Study participants will be monitored for injection site reactions. All injection site reactions will be recorded as AEs and further characterized.

8.3 Adverse Events and Serious Adverse Events

The PI is responsible for ensuring that all staff involved in the study are familiar with the content of this section.

The definitions of an AE or SAE are given in [Appendix B](#).

AEs will be reported by the participant (or, when appropriate, by a caregiver, surrogate, or the participant's legally authorized representative).

The investigator and any designees are responsible for detecting, documenting, and recording events that meet the definition of an AE.

8.3.1 Time Period and Frequency for Collecting Adverse Event and Serious Adverse Event Information

Non-serious AEs will be collected from the time of randomization throughout the treatment period and including the follow-up period.

Serious adverse events will be recorded from the time of signing of the first ICF (either the brief, pre-screening ICF or the full, screening ICF) throughout the treatment period and including the follow-up period.

If the investigator becomes aware of an SAE with a suspected causal relationship to the investigational product that occurs after the end of the clinical study in a participant treated by him or her, the investigator shall, without undue delay, report the SAE to the sponsor.

8.3.2 Follow-up of Adverse Events and Serious Adverse Events

Any AEs that are unresolved at the participant's last AE assessment in the study are followed up by the investigator for as long as medically indicated, but without further recording in the eCRF. The sponsor retains the right to request additional information for any participant with ongoing AE(s)/SAE(s) at the end of the study, if judged necessary.

Adverse event variables

The following variables will be collected for each AE:

- AE (verbatim)
- The date when the AE started and stopped
- Maximum intensity
- Whether the AE is serious or not
- Whether the AE is an injection site reaction
- Investigator causality rating against the investigational product (yes or no)
- Action taken with regard to investigational product
- AE caused participant's discontinuation of IP administration (yes or no)
- Outcome

In addition, the following variables will be collected for SAEs:

- Date AE met criteria for serious AE
- Date investigator became aware of serious AE
- AE is serious due to
- Date of hospitalization
- Date of discharge
- Probable cause of death
- Date of death

- Autopsy performed
- Causality assessment in relation to study procedure(s)
- Causality assessment to other medication

8.3.3 Causality Collection

The investigator should assess causal relationship between investigational product and each AE, and answer ‘yes’ or ‘no’ to the question ‘Do you consider that there is a reasonable possibility that the event may have been caused by the investigational product?’

For SAEs, causal relationship should also be assessed for other medication and study procedures. Note that for SAEs that could be associated with any study procedure, the causal relationship is implied as ‘yes’.

A guide to the interpretation of the causality question is found in [Appendix B](#).

8.3.4 Adverse Events Based on Signs and Symptoms

All AEs spontaneously reported by the participant or care provider, reported in response to an open question from the study site staff (ie, Have you had any health problems since the previous visit/you were previously asked?), or revealed by observation, will be collected and recorded in the eCRF. When collecting AEs, the recording of diagnoses is preferred (when possible) to recording a list of signs and symptoms. However, if a diagnosis is known and there are other signs or symptoms that are not generally part of the diagnosis, the diagnosis and each sign or symptom will be recorded separately.

In addition, the recording of CV events (in this study to include CV death, MI, stroke, coronary revascularization, and heart failure hospitalization) are important efficacy measures in CV clinical trials. All CV events will be recorded as AEs to allow for further characterization. Although this study will not be powered for these endpoints, the study will explore the effect of MEDI6570 on these important parameters.

8.3.5 Adverse Events Based on Examinations and Tests

The results from the CSP-mandated laboratory tests and vital signs will be summarized in the CSR.

Deterioration from baseline in protocol-mandated laboratory values or vital signs should therefore only be reported as AEs if they fulfill any of the SAE criteria, are the reason for discontinuation of treatment with the investigational product or are considered to be clinically relevant as judged by the investigator (which may include but not limited to consideration as to whether treatment or non-planned visits were required or other action was taken with the study treatment [eg, dose adjustment or drug interruption]).

If deterioration in a laboratory value/vital sign is associated with clinical signs and symptoms, the sign or symptom will be reported as an AE and the associated laboratory result/vital sign will be considered as additional information. Wherever possible, the reporting investigator uses the clinical, rather than the laboratory term (eg, anemia versus low hemoglobin value). In the absence of clinical signs or symptoms, clinically relevant deteriorations in non-mandated parameters should be reported as AE(s).

Any new or aggravated clinically relevant abnormal medical finding at a physical examination as compared with the baseline assessment will be reported as an AE unless unequivocally related to the disease under study.

8.3.6 Hy's Law

Cases where a participant shows elevations in liver biochemistry may require further evaluation and occurrences of AST or ALT $\geq 3x$ ULN together with TBL $\geq 2x$ ULN may need to be reported as SAEs. Further instruction on cases of increases in liver biochemistry and evaluation of Hy's Law is given in [Appendix E](#).

8.3.7 Reporting of Serious Adverse Events

All SAEs have to be reported, whether or not considered causally related to the investigational product, or to the study procedure(s). All SAEs will be recorded in the eCRF.

If any SAE occurs in the course of the study, then investigators or other site personnel inform the sponsor's appropriate representatives within 1 day, ie, immediately but **no later than 24 hours** after he or she becomes aware of it.

The designated AstraZeneca representative works with the investigator to ensure that all the necessary information is provided to the sponsor's Patient Safety data entry site **within 1 calendar day** of initial receipt for fatal and life-threatening events **and within 5 calendar days** of initial receipt for all other SAEs.

For fatal or life-threatening AEs where important or relevant information is missing, active follow-up is undertaken immediately. Investigators or other site personnel inform the sponsor's representatives of any follow-up information on a previously reported SAE within 1 calendar day, ie, immediately but **no later than 24 hours** after he or she becomes aware of it.

Once the investigators or other site personnel indicate an AE is serious in the electronic data capture system, an automated email alert is sent to the sponsor's designated representative.

If the electronic data capture system is not available, then the investigator or other study site staff reports an SAE to the appropriate sponsor representative by telephone.

The sponsor's representative will advise the investigator/study site staff how to proceed.

For further guidance on the definition of an SAE, see [Appendix B](#).

The reference document for definition of expectedness/listedness is the IB for the study intervention.

8.3.8 Pregnancy

All pregnancies and outcomes of pregnancy should be reported to the sponsor except if the pregnancy is discovered before the study participant has received any study intervention.

8.3.8.1 Maternal Exposure

Women of childbearing potential are not allowed to be included in this study. Should a pregnancy still occur, the investigational product should be discontinued immediately, and the pregnancy reported to the sponsor.

Pregnancy itself is not regarded as an AE. Congenital abnormalities/birth defects and spontaneous miscarriages should be reported and handled as SAEs. Elective abortions without complications should not be handled as AEs. The outcome of all pregnancies (spontaneous miscarriage, elective termination, ectopic pregnancy, normal birth or congenital abnormality) should be followed up and documented even if the participant was discontinued from the study.

If any pregnancy occurs during the study, then the investigator or other site personnel informs the appropriate sponsor representatives within 1 day, ie, immediately but **no later than 24 hours** after he or she becomes aware of it.

The sponsor's designated representative works with the investigator to ensure that all relevant information is provided to the sponsor's Patient Safety data entry site within 1 or 5 calendar days for SAEs (Section [8.3.7](#)) and within 30 days for all other pregnancies.

The same timelines apply when outcome information is available.

8.3.8.2 Paternal Exposure

Nonsterilized male study participants should be advised to use a condom for all sexual intercourse with a female partner of childbearing potential from Day 1 through the end of the study follow-up period. All male participants should refrain from fathering a child or donating sperm during the study and for 190 days following the last dose. If the partner becomes pregnant, the partner will be asked (under a separate consent) to provide information about the pregnancy and newborn baby.

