Randomization to the CCI dose group was removed.	
• To reduce the overall sample size of the study• The current number of participants in the [REDACTED] mg dose group is expected to provide sufficient dose-response information on the PK-PD relationship and endpoints, and is unlikely to be the dose with the optimal clinical risk-benefit balance.	Section 1.1 Synopsis; Section 1.2 Schema; Section 4.1 Overall Design; Section 4.3 Justification for Dose; Section 6.1 Study Interventions Administered, Table 8 Investigational Products; Section 6.2.3 Dose Preparation Steps, Table 9 Dose Preparation for Fixed SC Doses of CCI [REDACTED] and CCI [REDACTED] mg MEDI6570 and Placebo; Section 6.3.1 Randomization Procedure; Section 6.3.2 Blinding Procedure; Section 6.3.3 Unblinding for Interim Analysis Purposes (section deleted); Section 9.2 Sample Size Determination; Section 9.5 Interim Analyses

Table 1 Substantial Changes to the Protocol

Description of Change	Brief Rationale	Sections Affected
The number of participants was reduced from 792 to 400. CC1 	To reduce the overall sample size and improve feasibility of completion while maintaining acceptable power to inform development program decisions	Section 1.1 Synopsis; Section 1.2 Schema; Section 4.1 Overall Design; Section 9.2 Sample Size Determination
The 2 formal interim analyses were removed.	The interim analyses were administrative in nature. The full study results will be used for decision making on future development options. The study was designed to continue to completion regardless of the results of the interim analyses.	Section 1.1 Synopsis; Section 1.2 Schema; Section 4.1 Overall Design; Section 6.3.3 Unblinding for Interim Analysis Purposes (section deleted); Section 9.4.1 General Considerations; Section 9.5 Interim Analyses
The Day 405 visit (formerly Visit 16) was removed and the Day 325 visit (Visit 14) (formerly Day 334 [Visit 15]) is the new End of Study Visit	The safety follow-up visit will be performed approximately 3 months after the last dose (shortened from 6 months). CC1 	Section 1.1 Synopsis; Section 1.3 Schedules of Activities, Table 5 Schedule of Activities: Follow-up Period; Section 4.1 Overall Design

Table 1 Substantial Changes to the Protocol

Description of Change	Brief Rationale	Sections Affected

 • CCI [REDACTED] • [REDACTED] • [REDACTED] • [REDACTED] 		

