
The following new text was added to the Pregnancy section:
 
‘Nonsterilized male study participants should be advised to use a condom for all sexual intercourse with a female partner of childbearing potential from Day 1 through the end of the study follow-up period. All male participants should refrain from fathering a child or donating sperm during the study and for 190 days following the last dose. If the partner becomes pregnant, the partner will be asked (under a separate consent) to provide information about the pregnancy and newborn baby.’
 
In addition, the order of paragraphs in the section was re-arranged to match the template.
	
AstraZeneca has reassessed the theoretical risk to women of childbearing potential of exposure to semen from male participants receiving MEDI6570. The reassessment confirms that semen from male participants exposed to MEDI6570 poses low to no risk to the fetus of pregnant sexual partners or the potential fetus of sexual partners who may become pregnant. However, as a conservative and cautionary approach, following the AstraZeneca and Clinical Trial Facilitation Group guidelines, AstraZeneca has decided to update the clinical study protocol accordingly.
	
Section 8.3.8 Pregnancy; Section 8.3.8.1 Maternal Exposure (new section created with existing text); Section 8.3.8.2 Paternal Exposure (new text added to new section)

The following text was removed:
 
‘For the biomarker samples collected at Day 1 (Visit 3), Day 29 (Visit 5) and Day 85 (Visit 7) for CCI [REDACTED] NT-proBNP, CCI [REDACTED] part of each sample will be reserved for exploratory subgroup analysis for predicting response to therapy in primary, secondary, and exploratory endpoints’
	
Analyses will not be performed
	
Section 8.6.1 Collection of Mandatory Samples for Biomarker Analysis

The wording of the alternative hypothesis was amended as follows:
 
‘The alternative hypothesis is that there is a difference in this endpoint in participants given MEDI6570 compared with placebo the change from baseline in NCPV_{MD} reduction is larger in the MEDI6570 CCI mg group compared with the pooled placebo group.’
	
To reflect the change from 2-sided analyses to 1-sided analyses
	
Section 9.1 Statistical Hypotheses

ADA, anti-drug antibody(ies); CTA, computed tomography angiography; CV, cardiovascular;
ECG, electrocardiogram; **CCI** [REDACTED] hs-CRP, high sensitivity

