Disclosure Statement: This is a parallel-group, treatment study with 6 intervention groups (including the legacy **CCI** mg dose group and matched placebo) that is participant- and investigator-blinded.

Number of Participants: Approximately 400 participants will be randomly assigned to a study intervention, with an anticipated 369 participants being randomized to receive active study intervention (123 participants in each of the 2 MEDI6570 groups), and 123 participants being randomized across the 3 placebo groups (ie, including participants already randomized to the legacy dose/volume-matched placebo group for the **CCI** mg dose). It is estimated that approximately 360 evaluable participants (111 evaluable participants in each of the 2 MEDI6570 groups [**CCI** and **CCI** mg], plus 27 evaluable participants in the legacy **CCI** mg MEDI6570 group, plus 111 participants across the 3 placebo groups) will complete the study. Evaluable participants are defined as those with an evaluable CTA at baseline and follow-up (Day 253; Visit 13).

Intervention Groups and Duration: The study intervention is MEDI6570, a human Immunoglobulin G1 lambda (IgG1 λ) triple mutation antibody that binds to **CCI** **CCI** Going forward from Amendment 2, the study will include 4 intervention groups: **CCI** and **CCI** mg MEDI6570, and 2

injection/volume-matched placebo groups, while the participants previously randomized to [REDACTED] mg MEDI6570 or its injection/volume-matched placebo will continue their assigned treatment to the end of the study. Participants will be enrolled in the study for up to approximately 12 months, comprising an optional pre-screening period of up to 42 days (6 weeks), a screening and pre-randomization period of up to 42 days (6 weeks), an intervention period of 225 days (31 to 32 weeks), and a follow-up period of 100 days (approximately 14 weeks). Doses of MEDI6570 or placebo will be administered in the clinic SC Q4W for 32 weeks (9 doses in total).

Data Monitoring Committee: Yes

Statistical Methods:

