Table 4 Schedule of Activities: Intervention Period

Procedure	Visit:	3	4	5	6	7	8	9	10	11	12	Notes	Details in CSP section or appendix
	Day (± 7): ^a	1	10 ^a	29	57	85	113	141	169	197	225		
Observational period		X		X								Participant must be in clinic for 2 hours after dosing.	Section 8.2.5.2
Assessment of AEs/SAEs		X	X	X	X	X	X	X	X	X	X		Section 8.3
Concomitant medications		X	X	X	X	X	X	X	X	X	X		Section 6.5
Assess for injection site reactions		X		X	X	X	X	X	X	X	X		Section 8.2.5.3

^a The visit window is ± 7 days for dosing visits and ± 3 days for non-dosing visits (ie, Day 10 [Visit 4]). If a participant is dosed outside of the visit window, he or she should return to the initial planned schedule for subsequent visits.

AE, adverse event; CSP, Clinical Study Protocol; CV, cardiovascular; ECG, electrocardiogram; HIV, human immunodeficiency virus; CCI [REDACTED]

NT-proBNP, N-terminal prohormone brain natriuretic peptide; PK, pharmacokinetic(s); SAE serious adverse event; CCI [REDACTED]

Table 5 Schedule of Activities: Follow-up Period

Procedure	Visit:	13	14	Notes	Details in CSP section or appendix
	Day:	253 (- 4 to + 11 days)	325 (± 7 days)		
End of study visit			X		Section 4.3
Full physical examination			X		Section 8.2.1
Weight			X		Section 8.2.1
Vital signs		X	X	Whenever vital signs and blood draws are scheduled for the same nominal time, the blood draws should occur last.	Section 8.2.2

Table 5 Schedule of Activities: Follow-up Period

Procedure	Visit:	13	14	Notes	Details in CSP section or appendix
	Day:	253 (- 4 to + 11 days)	325 (± 7 days)		
ECGs		X	X		Section 8.2.3
Assessment of AEs/SAEs		X	X		Section 8.3
Concomitant medications		X	X		Section 6.5
Collect blood for:					
Clinical safety (clinical chemistry and hematology)		X	X		Section 8.2.4
PK		X	X		Section 8.5.1
CCI		X	X	Sample collected on Day 325 will be stored.	Section 8.6.1
CCI NT-proBNP		X			Section 8.6.1
Circulating biomarkers of inflammation CV disease		X			Section 8.6.1
Immunogenicity		X	X		Section 8.5.2
Creatinine for calculating eGFR		X		should occur within 30 days before the CTA; either local laboratory or point of care testing can be used.	Section 8.2.4
Collect urine for:					
Future use (optional)		X		Sample will be collected and stored.	Section 8.6.2
Echocardiogram		X			Section 8.1.1 and 8.1.2 (including instructions for repeating uninterpretable

Table 5 Schedule of Activities: Follow-up Period

Procedure	Visit:	13	14	Notes	Details in CSP section or appendix

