7 DISCONTINUATION OF STUDY INTERVENTION AND PARTICIPANT DISCONTINUATION/WITHDRAWAL

7.1 Discontinuation of Study Intervention

It may be necessary for a participant to discontinue study intervention temporarily or permanently. An individual participant will discontinue study intervention (either temporarily or permanently) if any of the following occurs in the participant in question:

- 1 An AE that in the opinion of the investigator or the sponsor contraindicates dosing.
- 2 Clinical symptoms of spontaneous bleeding so that the PI judges further administration of study intervention should be paused or stopped.
 - (a) Providers should consider temporary or permanent discontinuation of study intervention in participants who:
 - (i) Develop a condition that requires the use of chronic therapeutic anticoagulation therapy.
 - (ii) Experience severe bleeding that is not readily explained by a reversible alternate etiology. All bleeding events should be treated and followed up according to local clinical practice. Study intervention may be resumed when the risk of bleeding is deemed low in the judgment of the investigator.
 - (b) Study intervention must be stopped in the event of severe thrombocytopenia (platelet count < 50000 platelets/ μ L) which does not resolve, or if after resolution the investigator thinks it is not appropriate to restart study intervention because it may put the participant at undue risk.
- 3 A generalized hypersensitivity reaction occurring which, in the opinion of the PI and/or the Medical Monitor, would warrant discontinuation.
- 4 After initial dosing, there exists a clinically significant safety issue based on information not known or not disclosed before randomization.
- 5 Participant non-compliance that, in the opinion of the investigator or sponsor, warrants withdrawal (eg, refusal or inability to adhere to scheduled visits).
- 6 Withdrawal of consent.

If study intervention is permanently discontinued, the participant will remain in the study to be evaluated for protocol-specified assessments including follow-up of any AEs unless consent is withdrawn from further study participation (Section 7.2) or the participant is lost to follow-up (Section 7.3).

Note that discontinuation from study intervention is NOT the same as a withdrawal from the study.

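### Protocol 8.3.8.2 ends the condom advice at the end of follow-up (nominally Day 325), about 90 days before its own 190-day no-fathering restriction ends (nominally Day 415)

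*Protocol*

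**What the plan says.** Protocol 8.3.8.2 (Paternal Exposure) gives two instructions in consecutive sentences.

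- Non-sterilised men are advised to use a condom with a female partner of childbearing potential "from Day 1 through the end of the study follow-up period".
- All male participants are told to "refrain from fathering a child or donating sperm during the study and for 190 days following the last dose".

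The first period is tied to the visit schedule and the second to the last dose. The Synopsis (1.1) sets "a follow-up period of 100 days (approximately 14 weeks"), and Table 5 in 1.3 places the end-of-study visit at Day 325 (±7 days).

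Both sentences entered together under Amendment 2. The summary of changes gives one rationale for the whole insertion: a reassessment found that "semen from male participants exposed to MEDI6570 poses low to no risk to the fetus" of a pregnant partner, or the potential fetus of a partner who may become pregnant, and the text was added as a precaution. The same amendment brought the final visit forward: "The safety follow-up visit will be performed approximately 3 months after the last dose (shortened from 6 months").

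**The concern.** The condom is the only practical measure that 8.3.8.2 names. For a man who completes dosing, the advice to use it stops while he is still under the sponsor's instruction not to father a child. Nothing else in the protocol or SAP text available for review extends the condom advice, names another method for the remaining time or explains the shorter period.

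A site that counsels from the text as written would tell these men that condom use ends with the final visit. Table 5 schedules no contact after that visit, so it is the last planned occasion to advise them, with about three months of the restriction still to run.

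What is at stake is the clarity of a precautionary safety instruction. The trial's estimates are not touched.

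**Working it through.** This is day arithmetic only.

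**Inputs**

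- Doses: 9, every 28 days from Day 1 (Protocol 4.1; Table 4 in 1.3; SAP 3.4).
- End-of-study visit: Day 325 ± 7 (Table 5 in 1.3).
- Dosing windows: "The visit window is ± 7 days for dosing visits" (Table 4, footnote a).
- Restriction: 190 days after the last dose (8.3.8.2).

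**The plan's own figure.** Last dose = 1 + 8 × 28 = Day 225. Follow-up = 325 − 225 = 100 days, which matches the stated length.

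**Nominal gap**

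- Condom advice ends at Day 325.
- Restriction ends at 225 + 190 = Day 415.
- Gap = 415 − 325 = 90 days.

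**Range across the visit windows.** The last dose can fall on Day 218 to 232 and the final visit on Day 318 to 332.

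- Smallest gap: 218 + 190 − 332 = 76 days.
- Largest gap: 232 + 190 − 318 = 104 days.

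**Men who stop dosing early.** Section 7.1 keeps them under observation: "If study intervention is permanently discontinued, the participant will remain in the study to be evaluated for protocol-specified assessments". If they stay to Day 325, the gap is max(0, last dose day + 190 − 325).

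| Last dose | Day of last dose + 190 | Gap (days) |
|---|---|---|
| Day 113 or earlier | 303 or earlier | 0 |
| Day 141 | 331 | 6 |
| Day 169 | 359 | 34 |
| Day 197 | 387 | 62 |
| Day 225 | 415 | 90 |

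**Context.** Against the former final visit at Day 405, the nominal difference would have been 415 − 405 = 10 days.

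**The case against.** The strongest reply is that nothing here conflicts. A man can follow both sentences, and the second one covers the whole 190 days, so the restriction itself has no hole in it. That is right, and it is why the point is minor. What remains is that the only measure offered to help him comply stops early.

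A second reply is that the sentences may serve different ends. Condoms limit a partner's exposure to semen, while the other rule limits conception and sperm donation, and the two sentences address different groups of men. This is plausible, but the protocol does not say it. The amendment rationale is shared by both sentences, and the condom sentence is confined to partners of childbearing potential. If two durations are intended, the reader needs to be told.

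Third, some relevant material is out of sight. The rationale cites sponsor and external guidelines that could not be consulted, and the consent pages were not available. The statement that nothing extends the advice therefore covers only the text reviewed.

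Fourth, the Day 405 comparison is hypothetical. The paternal text was new in the amendment that removed that visit, so no version shown paired the two. It gives context for the size of the gap and does not show how the gap arose.

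Finally, the days counted are calendar time and not risk, which the sponsor puts at low to none. That limits the severity but leaves the mismatch in place.

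**Conclusion.** The concern holds as a low-severity safety inconsistency. For non-sterilised men with a female partner of childbearing potential who receive all 9 doses, the condom advice ends 90 days before the restriction does on the nominal schedule, and 76 to 104 days before it within the permitted windows. For men who stop dosing early the gap shrinks, and it is zero if the last dose is at Day 113 or before.

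These figures assume that the end of follow-up means the end-of-study visit and that men who stop dosing early remain in follow-up to Day 325. The number of men affected is not given in the documents. Sample size, endpoints, visits and analyses are unaffected.

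**What to change.** Reword the condom sentence in 8.3.8.2 so that the advice runs from Day 1 to the end of follow-up or to 190 days after the last dose, whichever is later. The later-of rule matters: for men whose last dose is at Day 113 or earlier, 190 days expire before Day 325, and a plain 190-day rule would shorten the advice they have now. If the safety team prefers a shorter condom period, it should state the reason in the same section.

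The cost is a longer condom instruction for these men, one line of protocol text and a matching change to the consent form if it carries the same wording.
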